2.5.3 Handling of missing values/censoring/discontinuations

Patients will be classified as non-responders if they fulful any of the following:

- Do not achieve remission within 12 weeks of Baseline
 - Note: Remission refers to the absence of flare.
- Are in the "escape arm"
 - Note: This refers to the patient entering escape between Baseline and Week 28.
- Prematurely discontinue study treatment prior to Week 28
 - Note: Absence of flare is checked prior to study treatment administration.
- Do not have information to evaluate sustained remission response until Week 28

Patients receiving less than the full amount of prednisolone for GCA as required by the taper, e.g. due to missing tablets, will not be classified as non-responders with the exception of those who are classified as non-adherent to the prednisolone taper regimen (refer to Section 2.5.1 for definition of adherence to the prednisolone taper regimen). Note: The final decision on whether the patient is non-adherent to the prednisolone taper will be confirmed by the blinded medical team on a by-patient basis in a BDRM prior to CDBL. This decision will be documented in the associated BDRM minutes.

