#### **4.1 Inclusion criteria**

Patients eligible for inclusion in this study must meet all of the following criteria:

1. Signed informed consent must be obtained prior to participation in the study.
2. Patient must be able to understand and communicate with the investigator and comply with the requirements of the study.
3. Male or non-pregnant, non-lactating female patients at least 50 years of age.
4. Diagnosis of GCA classified according to the following criteria:
  - Age at onset of disease  $\geq$  50 years.
  - History of ESR  $\geq$  30 mm/hr or CRP  $\geq$  10 mg/L.
  - Unequivocal cranial symptoms of GCA (new-onset localized headache, scalp or temporal artery tenderness, ischemia-related vision loss, or otherwise unexplained mouth or jaw pain upon mastication) **AND/OR** symptoms of polymyalgia rheumatica (PMR defined as shoulder and/or hip girdle pain associated with inflammatory morning stiffness).
  - Temporal artery biopsy revealing features of GCA **AND/OR** evidence of large-vessel vasculitis by angiography or cross-sectional imaging study such as magnetic resonance angiography (MRA), computed tomography angiography (CTA), positron emission tomography-computed tomography (PET-CT), or ultrasound.
5. Patients with new onset GCA or relapsing GCA:
  - Definition new onset: diagnosis of GCA within 6 weeks of Baseline Visit.
  - Definition relapsing GCA: diagnosis of GCA (in accordance with inclusion criterion no. 4)  $>$  6 weeks before Baseline Visit and in the meantime achieved remission (absence of signs and symptoms attributable to GCA and normalization of ESR ( $<$  30 mm/hr) and CRP ( $<$  10.0 mg/L) included) including previous treatment with  $\geq$  25 mg/day prednisolone equivalent for  $\geq$  2 weeks.
6. Active disease as defined by the presence of signs and symptoms of GCA (cranial or PMR) and elevated ESR  $\geq$  30 mm/hr, or CRP  $\geq$  10 mg/L, attributed to active GCA within 6 weeks of Baseline.
7. Prednisolone dose of 25-60 mg/day at Baseline.
8. Patients taking MTX ( $\leq$  25 mg/week) are allowed to continue their medication provided they have taken it for at least 3 months and are on a stable dose for at least 4 weeks prior to randomization and if they are on a stable folic acid treatment before randomization.

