## 6.3 Efficacy

### 6.3.1 Primary efficacy assessment

The primary efficacy objective is to evaluate the efficacy of secukinumab compared to placebo, in combination with a 26-week prednisolone taper regimen, based on the proportion of patients with GCA who have sustained remission.

The primary efficacy endpoint is the proportion of GCA patients in sustained remission (as defined below) at Week 28.

Definition of remission: Absence of flare (see below). Definition of sustained remission: patients without flare (see below) until Week 28 and in adherence to the protocol prednisolone taper regimen.

Definition of flare: Determined by the investigator and defined as the recurrence after remission of signs or symptoms of GCA (see [Section 6.3.1.1](#)) and/or ESR  $\geq 30$  mm/hr (see [Section 6.4.5.5](#)) and/or CRP  $\geq 10$  mg/L (see [Section 6.4.5.4](#)) attributable to GCA.

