### 9.4.3 Handling of missing values/censoring/discontinuations

Patients who (1) do not achieve remission within 12 weeks of Baseline; or (2) are in the “escape arm”; or (3) drop out from the study prior to/on Week 28, or (4) do not have information to evaluate sustained remission response at Week 28, will be classified as non-responders in the primary analysis. Patients receiving less than the full amount of

prednisolone as required by the taper, e.g. due to missing tablets, will not be classified as non-responders.

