1.1 Study design

This is a randomized, parallel-group, double-blind, placebo-controlled, multicenter, phase II study designed to evaluate the efficacy of secukinumab compared to placebo in combination with a 26-week prednisolone taper regimen in terms of sustained remission in patients with newly diagnosed or relapsing GCA who are naïve to biological therapy.

The study will consist of 6-week (maximum duration) screening period, a 52-week treatment period and an 8-week safety follow-up period (Figure 1-1).

Figure 1-1 Study design

Patients who do not achieve remission by Week 12, experience a flare after remission or cannot adhere to the prednisolone taper regimen will enter "escape". Upon entering "escape", patients will receive prednisolone at a dose determined by the physician's clinical judgment and continue to receive secukinumab or placebo in a blinded manner. Patients in "escape" should continue to attend all subsequent scheduled visit assessments.

As outlined in the protocol, most flares occurred within the first 6 months in the GiACTA trial (Stone et al 2017). Therefore, the time point for the primary analysis of this study is at Week 28, to evaluate the effect of secukinumab in patients who are on study treatment or placebo for 24 weeks.

At the randomization visit (Baseline) all eligible patients will be given a randomization number that assigns them to one of the following 2 arms in a 1:1 ratio:

- Group 1: secukinumab 300 mg s.c. + 26-week prednisolone taper regimen
- Group 2: placebo s.c. + 26-week prednisolone taper regimen

The patient randomization list was produced by or under the responsibility of Novartis Biometry using a validated system ensuring assignment of treatment arms to randomization numbers in the specified ratio. The randomization scheme was reviewed and approved by a member or delegate of the Novartis Biometry Randomization Group. It is planned to randomize at least 25 patients per treatment group.

Patients will receive secukinumab/placebo at Baseline, Week 1, 2, 3, 4, then every 4 weeks thereafter through to Week 48 (last dose) at the study center. Assessments will be performed in accordance to the study schedule. Patients in both groups will follow the protocol-defined prednisolone taper regimen.

In total, three interim analyses (IAs) will be conducted unless deemed unwarranted by the study team:

- First interim analysis (IA1): after approximately 50% of patients reach Week 28

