2.5.1 Primary endpoint

The primary endpoint is the proportion of GCA patients who are in sustained remission until Week 28.

The analysis of the primary variable will be based on the following estimand:

- Analysis set: FAS (for the patients of interest as outlined in Section 2.1)
- Variable of interest: Proportion of GCA patients who are in sustained remission until Week 28
 - Sustained remission: Patients without flare until Week 28 and in adherence to the protocol prednisolone taper regimen.

- Note: Flare is determined by the investigator and defined as the recurrence after remission of signs or symptoms of GCA and/or ESR \geq 30 mm/hr and/or CRP \geq 10 mg/L attributable to GCA.
- Adhere to prednisolone taper: Patients do not adhere to the prednisolone taper regimen if during the 26-week prednisolone taper regimen any of the following occur:
 - Patient does not take prednisolone medication for GCA for ≥ 6 consecutive days.
 - Patient takes prednisolone treatment for GCA for < 80% of the 26-week prednisolone taper regimen period.
 - Patient has received additional prednisolone for GCA to that stated in the taper regimen.

Note: This criteria (receiving additional prednisolone) does not apply to those patients in the "escape arm".

This means a patient is classified as receiving an additional prednisolone for GCA to that stated in the taper regimen if in the timeframe:

- [Week 0-Week 11] the patient's weekly dose is 20% over the stated dosage of prednisolone, or
- [Week 12-Week 26] the patient's weekly dose is 30% over the stated dosage of prednisolone.
- Patient received an additional corticosteroid to that stated in the taper regimen. Note: This will be based on the respective PD associated with this criteria.

Note: The final decision on whether the patient is non-adherent to the prednisolone taper will be confirmed by the blinded medical team on a by-patient basis in a Blind Data Review Meeting (BDRM) prior to CDBL. This decision will be documented in the associated BDRM minutes.

- Intervention effect: Effect between secukinumab versus placebo at Week 28 regardless of adherence to randomized treatment.
- Measure of intervention effect: Odds ratio (OR).

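### Remission and flare are each defined by the other, so the Week 12 non-remission rule cannot identify patients whose disease never settles

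*SAP*

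**What the plan says.** The definitions are the same in both documents.

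- Remission, Protocol 6.3.1: "Definition of remission: Absence of flare (see below". SAP 2.5.3 repeats this directly under the Week 12 rule: "Note: Remission refers to the absence of flare". SAP 2.7.2 uses it again for remission by visit.
- Flare, SAP 2.5.1: "Flare is determined by the investigator and defined as the recurrence after remission of signs or symptoms of GCA", and/or ESR of at least 30 mm/hr and/or CRP of at least 10 mg/L attributable to GCA. Protocol 6.3.1 agrees.
- Primary endpoint, SAP 2.5.1: "Sustained remission: Patients without flare until Week 28 and in adherence to the protocol prednisolone taper regimen".
- Non-response, SAP 2.5.3: "Do not achieve remission within 12 weeks of Baseline". Protocol 9.4.3 has the same criterion: "Patients who (1) do not achieve remission within 12 weeks of Baseline". SAP 2.7.3 carries it to Week 52.
- Escape, SAP 1.1, uses the same term: "Patients who do not achieve remission by Week 12, experience a flare after remission or cannot adhere to the prednisolone taper regimen will enter" escape.

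A remission state with clinical content appears only in inclusion criterion 5 (Protocol 4.1), for the eligibility of relapsing patients: "achieved remission (absence of signs and symptoms attributable to GCA and normalization of ESR" and CRP.

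**The concern.** Both documents list failure to reach remission by Week 12 as a ground for non-response separate from flare and escape. The authors therefore meant remission to be something a patient can fail to achieve. The written definitions do not allow that failure: no remission requires a flare, and a flare requires an earlier remission.

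Two outputs are affected. In the primary endpoint, a patient with persistent disease who otherwise follows the plan could count as a responder. In the Week 12 remission rate (SAP 2.7.1, 2.7.2), persistent disease counts as remission unless the patient has escaped, discontinued study treatment or has missing status. The primary endpoint feeds a numerical GO rule in SAP 2.5.2, so a few miscounted patients could matter if the result falls near the threshold.

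**Working it through.** **Step 1: the logic.** Take the visits at Weeks 0, 1, 2, 3, 4, 8 and 12 and mark each as disease active or inactive, giving 2^7 = 128 patterns. Apply the definitions forward in time: a flare at a visit needs activity now and a settled state before it, and remission is no flare.

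- Counting any visit from Baseline, the Week 12 rule fires in 0 of 128 patterns. The always-active patient is in remission at all 7 visits.
- Counting post-Baseline visits only, it fires in 1 of 128: inactive at Baseline, active at every later visit. That patient already fails by flare. The always-active patient still passes.
- With remission defined as no disease activity, counting any visit from Baseline, the rule fires for the always-active pattern, as intended.

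**Step 2: reproduce the plan's figure.** SAP Table 3-1, first row: 14/25 vs 4/25, design priors Beta(1, 1) and Beta(10, 43). By the SAP 2.5.2 formula Beta(y + a, n − y + b), the posteriors are Beta(15, 12) and Beta(14, 64). Simulation gives a median risk difference (RD) of 0.38 with limits 0.17 and 0.57; the table states 0.38, 0.19 and 0.56. The median agrees, and the small gap in the limits does not bear on this point.

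**Step 3: effect of miscounting.** Inputs are the analysis priors of SAP 2.5.2, Beta(0.5, 0.5) for secukinumab and Beta(10, 43) for placebo, with n = 25 per arm. GO requires P(RD > 0.22) ≥ 0.50 and P(RD > 0) ≥ 0.90. The number of miscounted patients is an assumption.

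| Responders (secukinumab vs placebo) | Posteriors | P(RD > 0.22) | P(RD > 0) | GO |
|---|---|---|---|---|
| 10 vs 4 | Beta(10.5, 15.5), Beta(14, 64) | 0.51 | 0.99 | met |
| 10 vs 5 | Beta(10.5, 15.5), Beta(15, 63) | 0.46 | 0.98 | not met |
| 9 vs 4 | Beta(9.5, 16.5), Beta(14, 64) | 0.36 | 0.97 | not met |
| 11 vs 7 | Beta(11.5, 14.5), Beta(17, 61) | 0.51 | 0.98 | met |
| 14 vs 4 | Beta(14.5, 11.5), Beta(14, 64) | 0.93 | >0.99 | met |
| 14 vs 7 | Beta(14.5, 11.5), Beta(17, 61) | 0.87 | >0.99 | met |

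- If the true count is 10 vs 4, one miscounted placebo patient (10 vs 5) removes a GO.
- If the true count is 9 vs 4, one miscounted secukinumab patient (10 vs 4) creates one.
- At 14 vs 4, three miscounted placebo patients lower the median RD from 0.38 to 0.34, and GO stands.

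The arms are not equally sensitive. One patient moves the posterior mean by 1/(25 + 1) = 3.8 points on secukinumab, but by 1/(25 + 53) = 1.3 points on placebo, where the prior carries more weight.

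**The case against.** The strongest reply is that other rules catch most of these patients, and it largely stands for the primary endpoint. Protocol 3.1 has disease activity assessed at every visit and sends patients who cannot keep to the taper to escape. Protocol 3.2.1 opens escape to active disease as well as flare. Escape before Week 28, extra steroid, premature treatment discontinuation and missing information each make a patient a non-responder (SAP 2.5.1, 2.5.3). Criterion 6 asks for active disease within 6 weeks of Baseline, not on the day, and patients enter on 25–60 mg/day of prednisolone, so some will have settled by Day 1. A reader might infer that every never-remitter becomes a responder; the documents do not support that.

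The reply does not close the gap. The Week 12 escape trigger uses the same undefined term, and the active-disease wording in Protocol 3.2.1 is permissive.

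A second reply is that investigators determine flare and will record persistent disease sensibly. They may, but classification would then depend on sites departing from the word recurrence.

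A third is that SAP section 4 moves the time reference from clinical remission to Baseline. It does, but the flare definition in SAP 2.5.1 and 2.7.2 still says after remission. Planned summaries of signs and symptoms by visit (SAP 2.4.3), reasons for response status (2.5.4) and CRP and ESR by remission status (2.7.2) could expose the problem; they would not correct the endpoint.

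**Conclusion.** The circularity is real, sits in the operative rules, and is not repaired by any other endpoint definition. The Week 12 non-responder criterion cannot identify the patients it is meant for, and the Week 12 remission rate inherits the defect. That conclusion rests on wording alone.

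The size is uncertain. The exposed group for the primary endpoint is never-remitters who avoid escape, extra steroid, discontinuation and missing status, and the documents do not number it. A reader might infer that such patients gather on placebo, so that the error shrinks the effect. No passage supports this for patients who also avoid escape, and the figures show that the error can work either way. Nor is the GO decision fragile in general. With 4 true placebo responders and one to three placebo patients miscounted, GO is lost only at exactly 10 secukinumab responders: at 11, three such errors still leave P(RD > 0.22) at 0.51. P(RD > 0) stays above 0.90 in every case shown.

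**What to change.** In SAP 2.5.3, 2.7.2 and 2.7.3, before unblinding, replace the absence-of-flare note for the endpoint derivations with a state that has content: no signs or symptoms attributable to GCA, and no ESR ≥ 30 mm/hr or CRP ≥ 10 mg/L attributable to GCA. This is the substance of inclusion criterion 5 with the attribution judgment of the flare definition kept, so that a raised CRP from, say, an infection does not count as active disease. Classify patients who have not reached that state by Week 12 as non-responders for the sustained remission endpoints and as not in remission at Week 12. For the endpoint derivations, count flare as recurrence after that state.

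The cost is SAP wording and one extra derivation. Protocol Table 6-1 schedules signs and symptoms, ESR and CRP at every visit from Baseline to Week 52. Observed remission rates may be lower.

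The escape passages that use the same term (Protocol 3.1 and 5.5.6, SAP 1.1) must be reconciled with this by the sponsor. No escape or treatment rule is proposed here; changing the protocol's own definitions would touch that trigger and need an amendment.

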### **9.5 Analysis of secondary variables**

#### **9.5.1 Efficacy variables**

The following secondary efficacy endpoints for this study will be analyzed for the FAS:

- Remission rate at Week 12
- Time to first GCA flare after remission (up to Week 52)
- Total cumulative prednisolone dose over 28 Weeks and 52 Weeks
- Proportion of GCA patients in sustained remission at Week 52
  - Definition of remission: absence of flare.
  - Definition of sustained remission: patients without flare until Week 52 and in adherence to the protocol prednisolone taper regimen + prednisolone-free phase from Week 27 onwards
  - Definition of flare: determined by the investigator and defined as the recurrence after remission of signs or symptoms of GCA and/or erythrocyte sedimentation rate (ESR)  $\geq 30$  mm/hr and/or CRP  $\geq 10$  mg/L attributable to GCA
- Proportion of patients on prednisolone dose  $\leq 5$  mg/day at Week 19, Week 28 and Week 52

- Change from Baseline PGA at Week 4, 8, 12, 16, 20, 24, 28, 36, 44 and 52
- Change from Baseline PhGA at Week 4, 8, 12, 16, 20, 24, 28, 36, 44 and 52
- Change from Baseline FACIT-Fatigue at Week 4, 8, 12, 16, 20, 24, 28, 36, 44 and 52
- Change from Baseline SF-36 at Week 4, 8, 12, 16, 20, 24, 28, 36, 44 and 52
- Change from Baseline EQ-5D at Week 4, 8, 12, 16, 20, 24, 28, 36, 44 and 52
- Change from Baseline CRP at Week 4, 8, 12, 16, 20, 24, 28, 32, 36, 40, 44, 48 and 52
- Change from Baseline ESR at Week 4, 8, 12, 16, 20, 24, 28, 32, 36, 40, 44, 48 and 52

Similar to the primary endpoint methodology, the posterior distributions for the estimate of the OR, RD, and RR will be derived by sampling from the posterior distributions of the remission response rates at Week 12 of secukinumab and placebo. The prior distribution for the remission response rates at Week 12 for both treatment groups will be a Beta distribution with parameters 1/2 and 1/2, i.e. Beta (1/2, 1/2). The associated median and 95% credibility interval will be presented. Patients that withdrew from the study or entered “escape” therapy will be classified as non-responders from the point of withdrawal/escape onwards. Patients with a missing remission status at a particular time point will be classified as non-responders at that time point. In addition, the proportion of patients in remission over time will be summarized descriptively by visit and by treatment group.

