The time to first GCA flare after remission (up to Week 52) will be summarized using Kaplan Meier curves. Patients who:

- Withdraw from the study prior to Week 52 will be censored at the time of withdrawal
- Do not have a flare up to Week 52 will be censored at Week 52

Descriptive statistics will also be provided for time to first GCA flare after clinical remission (up to Week 52).

Total cumulative prednisolone dose over 28 and 52 weeks will be summarized over time by treatment group.

The proportion of GCA patients in sustained remission at Week 52 will be analyzed using the methods outlined in Section 9.4.2. Patients who (1) do not achieve remission within 12 weeks of Baseline; or (2) are in the “escape arm”; or (3) drop out from the study prior to/on Week 52, or (4) do not have information to evaluate sustained remission response at Week 52, will be classified as non responders. Patients receiving less than the full amount of prednisolone as required by the taper, e.g. due to missing tablets, will not be classified as non-responders.

The number (and percentage) of patients on prednisolone dose  $\leq$ 5mg/day at Week 19, 28 and 52 will be summarized by treatment group.

The continuous secondary efficacy endpoints (actual value and change from baseline value) will be summarized descriptively by visit (where applicable) and by treatment group.

For SF-36, the following variables will be evaluated:

- SF-36 domain scores

- SF-36 domain score responders
  - Type I responders (improvement of  $\geq 5$  points in  $\geq 6$  domains)
  - Type II responders (improvement of  $\geq 10$  points in  $\geq 3$  domains)
- SF-36 PCS and MCS scores
- SF-36 PCS and MCS score responders
  - Type I responders (improvement of  $\geq 2.5$  points)
  - Type II responders (improvement of  $\geq 5$  points)

The EQ-5D is a questionnaire with 5 questions (regarding mobility, self-care, usual activities, pain/discomfort, and anxiety/depression) each with three categories (no problem, moderate problem, severe problems) and a health state assessment from 0 (worst possible health state) to 100 (best possible health state) (see [Section 6.5.2.1.4](#) for further details). The number and percentage of subjects in each of the three categories for each question will be presented by visit and treatment group. Summary statistics will be provided for the health state assessment by visit and treatment group.

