2.3.1 Patient disposition

Patient disposition will be summarized using:

- Study treatment disposition
- Study disposition

Note: Patients may stop study treatment but continue to stay in the study hence there will be a differentiation between study treatment and study disposition. Patients will be analyzed according to the treatment assigned at the last randomization (see Section 2.2 for further details).

The number and percentage of patients who completed study treatment, those who discontinued study treatment prematurely, along with the primary reason for study treatment discontinuation, will be presented for each treatment group and overall (i.e. all patients) for the RAS.

A similar summary table will be presented for study disposition, i.e. the treatment disposition phase.

All patient disposition data will be listed by treatment group, center, and subject number for the RAS.

In additition, for the legal requirements of clinicaltrials.gov and EudraCT, the number and percentage of patients enrolled in each site will be provided.

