2.7.3 Handling of missing values/censoring/discontinuations

For sustained remission until Week 52, patients will be classified as non-responders if they fulful any of the following:

- Do not achieve remission within 12 weeks of Baseline
 - Note: Remission refers to the absence of flare.
- Are in the "escape arm"
 - Note: This refers to the patient entering escape between Baseline and Week 52.
- Prematurely discontinue study treatment prior to Week 52
 - Note: Absence of flare is checked prior to study treatment administration.
- Do not have information to evaluate sustained remission response until Week 52

Patients receiving less than the full amount of prednisolone for GCA as required by the taper, e.g. due to missing tablets, will not be classified as non-responders with the exception of those who are classified as non-adherent to the prednisolone taper regimen (refer to Section 2.5.1 for definition of adherence to the prednisolone taper regimen). Note: The final decision on whether

the patient is non-adherent to the prednisolone taper will be confirmed by the blinded medical team on a by-patient basis in a BDRM prior to CDBL. This decision will be documented in the associated BDRM minutes.

For remission rate at Week 12, patients will be classified as non-responders if they fulfil any of the following:

- Prematurely discontinue study treatment
- Enter "escape" therapy

Note: Patients will be classified as non-responders for the above two scenarios from the point of withdrawal/escape onwards. Patients with a missing remission status at Week 12 will be classified as non-responders.

For time to first GCA flare after remission (up to and including Week 52), patients who:

- Prematurely discontinue study treatment prior to Week 52 will be censored at the time of premature discontinuation
- Complete treatment and do not have a flare will be censored at their last visit in the treatment phase

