4 Change to protocol specified analyses

The baseline prednisolone dose subgroup categories have been updated from > 40 mg/day and ≤ 40 mg/day to ≥ 40 mg/day and < 40 mg/day to align with the planned prednisolone taper regimen.

Sustained remission at a timepoint refers to patients being without flare until that timepoint and in adherence to the protocol prednisolone taper regimen. As adherence to the protocol prednisolone taper regimen is a component of the sustained remission definition already; any redundant mention of adherence to prednisolone taper regimen has been removed throughout this document.

Any reference to the time point after clinical remission has been updated to be after Baseline; this aligns more clearly with what was planned to be analyzed.

5 Appendix

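### SAP 2.5.3 counts stopping the injections as failure, contradicting the stated primary estimand and the protocol's study drop-out rule; SAP 2.7.3 does the same for three secondary endpoints

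*SAP*

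**What the plan says.** **Estimand.** SAP 2.5.1 gives the intervention effect as "Effect between secukinumab versus placebo at Week 28 regardless of adherence to randomized treatment". Protocol 9.4.1 uses the same wording.

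**Primary non-responder rule.** Protocol 9.4.3 has four criteria: no remission by Week 12, escape, leaving the study, and missing Week 28 information. The criterion for leaving reads "3) drop out from the study prior to/on Week 28". SAP 2.5.3 keeps the other three but replaces this one with "Prematurely discontinue study treatment prior to Week 28".

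**Two different events.** SAP 2.1.1.1 defines study treatment as the secukinumab or placebo injections and calls prednisolone the co-administered treatment. SAP 2.3.1 notes "Patients may stop study treatment but continue to stay in the study" and reports the two dispositions separately. Protocol 5.6.2 says that stopping treatment does not require leaving the study, and encourages such patients to continue assessments.

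**Secondary endpoints.** For Week 12 remission, the rule in Protocol 9.5.1 begins "Patients that withdrew from the study or entered" escape. For time to first flare, Protocol 9.5.1 says of patients who "Withdraw from the study prior to Week 52 will be censored at the time of withdrawal"; SAP 2.7.3 instead says of patients who "Prematurely discontinue study treatment prior to Week 52 will be censored at the time of premature discontinuation".

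**Declared changes.** SAP Section 4 lists three, the first beginning "The baseline prednisolone dose subgroup categories have been updated". The others remove redundant adherence wording and change the time reference from clinical remission to Baseline. None concerns discontinuation.

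**The concern.** The SAP says that stopping the randomized drug does not matter to the effect being estimated, and then lets it decide the outcome. As written, the primary analysis estimates a composite in which stopping injections is failure, and it overwrites flare and taper data that the protocol sets out to collect after stopping. The result then depends on how these discontinuations split between the arms.

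For time to first flare the consequence is different. Flares observed after a patient stops injections are discarded, and the censoring may be informative in a direction the documents do not establish.

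Two governing texts would support two different Week 28 results, with about 25 patients per arm and a development decision resting on the posterior.

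**Working it through.** **1. The rules side by side**

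| Endpoint | Protocol (9.4.3, 9.5.1) | SAP (2.5.3, 2.7.3) |
|---|---|---|
| Sustained remission, Week 28 | leaves study: failure | stops injections: failure |
| Sustained remission, Week 52 | leaves study: failure | stops injections: failure |
| Remission, Week 12 | leaves study: failure | stops injections: failure |
| Time to first flare | censored on leaving study | censored on stopping injections |

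For the Week 28 and Week 52 endpoints the boundary also moves, from prior to or on the visit to prior to it.

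For Week 28, apart from that boundary, the rules disagree only for a patient who stops injections but stays in the study, is evaluable and flare-free, does not escape and keeps to the taper. The estimand is stated for the primary endpoint only, so the secondary endpoints conflict with Protocol 9.5.1 and not with an estimand.

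**2. Does a planned analysis recover the stated effect?** No. The supportive analyses in SAP 2.5.4 change the prior, the model or the flare components. The table of reasons counts affected patients but does not give the effect under the stated estimand. The by-visit remission table in SAP 2.7.2 stops four weeks after the last dose.

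**3. Inputs for the size.** n = 25 per arm and 14 versus 4 expected responders (SAP Section 3); rates 56% and 18%, and GO if P(RD > 0.22) ≥ 0.50 and P(RD > 0) ≥ 0.90 (SAP 2.5.2); priors Beta(0.5, 0.5) for secukinumab and Beta(10, 43) for placebo (SAP 2.5.2).

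**4. Reproducing the plan's own figure.** SAP Table 3-1, first row, uses Beta(1, 1) for secukinumab, so the posteriors are Beta(1+14, 1+11) and Beta(10+4, 43+21). Recomputed 2.5%, 50% and 97.5% points of p1 − p2: 0.17, 0.38, 0.57, with P(p1 > p2) = 0.9999. The plan gives 0.19, 0.38, 0.56 and 0.99. The median agrees and the limits are within 0.02. The difference in the limits has no bearing on this point.

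**5. Reclassifying k secukinumab responders at 14/25 versus 4/25.** Secukinumab posterior Beta(0.5 + 14 − k, 0.5 + 11 + k); placebo Beta(14, 64).

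| k | median RD | median OR | P(RD > 0.22) | P(RD > 0) | GO |
|---|---|---|---|---|---|
| 0 | 0.380 | 5.95 | 0.93 | > 0.99 | yes |
| 1 | 0.341 | 5.07 | 0.87 | > 0.99 | yes |
| 2 | 0.301 | 4.33 | 0.78 | > 0.99 | yes |
| 3 | 0.262 | 3.69 | 0.65 | > 0.99 | yes |
| 4 | 0.223 | 3.14 | 0.51 | 0.99 | yes, barely |
| 5 | 0.183 | 2.65 | 0.36 | 0.97 | no |

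The lower 95% limit of the OR goes from 2.27 at k = 0 to 0.96 at k = 5. Reclassifying one or two placebo responders instead raises the median RD to 0.393 or 0.406.

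**6. Chance of GO.** With a fraction f of would-be responders reclassified, the true rate becomes p × (1 − f). P(GO) is the sum, over all 26 × 26 outcomes meeting both criteria, of Bin(y1; 25, p1) × Bin(y2; 25, p2). The fractions are assumed.

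| True rates | Reclassified | True RD | P(GO) |
|---|---|---|---|
| 56% / 18% | none | 0.38 | 0.94 |
| 56% / 18% | 2% both arms | 0.37 | 0.93 |
| 56% / 18% | 5% both arms | 0.36 | 0.90 |
| 56% / 18% | 10% both arms | 0.34 | 0.86 |
| 56% / 18% | 20% both arms | 0.30 | 0.72 |
| 56% / 18% | 5% secukinumab only | 0.35 | 0.90 |
| 56% / 18% | 10% secukinumab only | 0.32 | 0.84 |
| 56% / 18% | 10% placebo only | 0.40 | 0.95 |

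At 48% (the lowest secukinumab rate in SAP Table 3-1) versus 18%, P(GO) is 0.78 with none reclassified, 0.71 at 5% and 0.64 at 10% in both arms.

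**The case against.** - **Few patients may be affected.** Many who stop injections will also flare, escape or lack data, and so fail under both rules. No rate is given. GO at 14/25 survives the loss of four responders (4/14 = 29%) and fails only at five (36%), and the GO rule is only guidance in a small Phase II trial. All of this stands. It limits the likely size but does not remove the contradiction.
- **It may be loose drafting.** For Week 12, SAP 2.7.3 lists stopping treatment and then refers to it as withdrawal, and neither SAP section has a separate item for leaving the study. Intent is therefore uncertain. But SAP 2.3.1 separates the events, and the note under the SAP 2.5.3 rule refers to checking for flare before dosing, which points to treatment. A programmer would follow the text.
- **Undeclared is judged on SAP Section 4.** The SAP's front pages were not available to check. The accurate statement is that Section 4, where such changes belong, does not list it.
- **A composite is legitimate and may suit patients who stop injections because they start another immunosuppressant.** Under the protocol's rule, such a patient who stays flare-free could count as a responder. This stands as a reason to state their classification. It does not justify keeping an estimand that says the opposite of the rule.

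**Conclusion.** The concern holds. The primary analysis in SAP 2.5.3 does not estimate the effect defined in SAP 2.5.1 and Protocol 9.4.1, and it departs from Protocol 9.4.3. SAP 2.7.3 departs from Protocol 9.5.1 for three secondary endpoints. This follows from the texts and depends on no figure.

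The practical size is unknown. At the planned counts each reclassified secukinumab responder lowers the median RD by about 0.04. The bias can go either way: it lowers the estimated benefit unless the losses fall mainly on placebo. The calculations assume that 56% and 18% are rates under the protocol's rule. The documents do not say whether those rates already count discontinuers as failures; if they do, part of the loss is already included.

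Because the rule defines the primary endpoint, it must be settled before the final analysis is unblinded.

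**What to change.** Choose one of two routes and write it into SAP 2.5.3, 2.7.3 and Section 4.

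1. **Keep the estimand.** Restore the protocol's rule (leaving the study), including its Week 28 and Week 52 boundaries. Use flare and taper data observed after injections stop, and censor time to first flare at study withdrawal. Keep the current SAP rule as a supportive analysis.
2. **Change the estimand.** Restate it as a composite with treatment discontinuation as failure, list the change in Section 4, and add the treatment-policy analysis as supportive.

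Under either route:

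- Align the four-week limit on the by-visit remission table in SAP 2.7.2 with the rule chosen.
- Reconcile Protocol 5.5.8, which lets a patient stay in the study after injections are permanently stopped for a prohibited treatment, with footnote 2 of Table 5-5, which says such agents require study discontinuation. State how these patients are classified in the analysis.

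The cost is SAP wording, a derivation flag, one extra supportive analysis and the adjustment to the by-visit table. Follow-up after stopping injections is only encouraged, so some of these patients will remain non-responders for lack of data.
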